## **8.4 Treatment of Overdose**

Not applicable.

## **8.5 Pharmacokinetics**

Pharmacokinetic parameters are not evaluated in this study.

## 8.6 Pharmacodynamics

Pharmacodynamic parameters are not evaluated in this study.

## 8.7 Genetics

Genetics are not evaluated in this study.

## 8.8 Biomarkers

Biomarkers are not evaluated in this study.

## 8.9 Medical Resource Utilisation and Health Economics

Medical Resource Utilisation and Health Economics parameters are not evaluated in this study.

# 9.0 STATISTICAL CONSIDERATIONS

## 9.1 Statistical Hypotheses

For the co-primary endpoints, a hierarchical procedure will be used to control the risk of concluding erroneously.

To demonstrate that the Hib response in Inv\_group is non-inferior to Com\_group, 1-month post-booster vaccination in terms of:

- GMCs
  - Criterion: Lower limit (LL) of the 2-sided 95% confidence interval (CI) on group GMC ratio (Inv\_group over Com\_group) is above 0.5.
- Percentage of subjects with anti-PRP antibody concentrations  $\geq 5 \mu\text{g/mL}$ .
  - Criterion: First primary objective is met and the LL of the 2-sided 95% CI on group difference in the percentage (Inv\_group minus Com\_group) is above -10%.

To demonstrate that the Hib response in Inv\_group is superior to Com\_group, 1-month post-booster vaccination in terms of:

- GMCs
  - Criterion: All previous objectives are met and the LL of the 2-sided 95% CI on group GMC ratio (Inv\_group over Com\_group) is above 1.
- Percentage of subjects with anti-PRP antibody concentrations  $\geq 5 \mu\text{g/mL}$ .
  - Criterion: All previous objectives are met and the LL of the 2-sided 95% CI on group difference in the percentage (Inv\_group minus Com\_group) is above 0.

## 9.2 Sample Size Determination

The study will enrol approximately 500 subjects in a 1:1 ratio. Assuming that 20% of the subjects would not be evaluable, the power was computed for 400 evaluable subjects (i.e., 200 subjects each in the Inv\_group and Com\_group). Evaluable is defined as: meeting all eligibility criteria, complying with the procedures defined in the protocol, and, therefore, qualified for inclusion in the according-to-protocol analysis.

A 2.5% nominal type I error was used for each co-primary evaluation. To control the overall type I error below 2.5%, a hierarchical procedure will be used for the multiple study objectives. The study has:

- More than 99% power to reach the first co-primary objective. This power is obtained from PASS 2012, 1-sided t-test (non-inferiority with 0.5 group ratio as margin, i.e., -0.301 in  $\log_{10}$  Scale) for 2 independent means with common 0.63 variance of  $\log_{10}$  transformed anti-PRP concentration, under the specific alternative that the group GMC ratio is 1.75 [Silfverdal, 2016], i.e., 0.2430 in  $\log_{10}$  scale, and
- More than 99% power to reach the second co-primary objective. This power is obtained from PASS 2012, 1-sided Miettinen and Nurminen [Miettinen, 1985] test (non-inferiority with -10% margin) for 2 independent proportions under the specific alternative that the proportions are 46% after *Vaxelis* and 62% after *Infanrix hexa* [Silfverdal, 2016] while accounting for the power to meet the first co-primary objective.
- Approximately 97% power to reach the third co-primary objective. This power is obtained from PASS 2012, 1-sided t-test (inequality) for 2 independent means with common 0.63 variance in  $\log_{10}$  scale, under the specific alternative that the group GMC ratio is 1.75 [Silfverdal, 2016], i.e., 0.2430 in  $\log_{10}$  scale while accounting for the power to meet the first co-primary objective.
- At least 80% power to reach all co-primary objectives. This power is obtained from PASS 2012, 1-sided Z test (inequality) with pooled variance for 2 independent proportions under the specific alternative that the proportions are 46% after *Vaxelis* and 62% after *Infanrix hexa* [Silfverdal, 2016] while accounting for the power to meet the first 3 co-primary objectives.

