### 9.4.3 Immunogenicity Analyses

The confirmatory analyses of non-inferiority will be based on the PPS while the confirmatory analyses of superiority will be based on the ES.

- Method for non-inferiority and superiority in anti-PRP antibody concentration at 1-month post-booster vaccination:

- The 2-sided 95% CI for group GMC ratio derived from an ANOVA model on  $\log_{10}$  transformed concentration will be used. The model will include country, maternal immunisation and group as fixed effects. (Missing data will not be replaced. Concentration below assay cut-off will be replaced by half the assay cut-off).
- Method for non-inferiority and superiority in the percentage of subjects with anti-PRP antibody concentration  $\geq 5.0 \mu\text{g/mL}$  at 1-month post-booster vaccination:
  - The 2-sided 95% CI on group difference in seroconversion rate (Inv\_group minus Com\_group) will be computed based on Miettinen and Nurminen method [[Miettinen, 1985](#)].
- Descriptive analysis for each study group will be provided by country for Anti-PRP antibody concentrations at 1-month post-primary vaccination, pre-booster and 1-month post-booster vaccination, and for the percentage of subjects with anti-PRP antibody concentration  $\geq 5.0 \mu\text{g/mL}$  at 1-month post-booster vaccination.

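### Section 9.2 labels 0.63 a variance, but the stated 97% power for GMC superiority fits 0.63 as a standard deviation; as a variance it gives 86.3%

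*Protocol*

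**What the plan says.** Section 9.2 of the protocol lists four hierarchical objectives and a power for each. The common inputs are stated: "the power was computed for 400 evaluable subjects", that is 200 per group, and "A 2.5% nominal type I error was used for each co-primary evaluation".

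The two GMC objectives share one dispersion figure. Bullet 1 (non-inferiority) is calculated "for 2 independent means with common 0.63 variance of" log10 anti-PRP concentration. Bullet 3 (superiority) uses a "1-sided t-test (inequality) for 2 independent means with common 0.63 variance" on the same scale. Both are computed "under the specific alternative that the group GMC ratio is 1.75", which the protocol converts to 0.2430 in log10 units.

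The results reported are more than 99% for bullet 1, "Approximately 97% power to reach the third co-primary objective" for bullet 3, and "At least 80% power to reach all co-primary objectives" for bullet 4. The last rests on 46% versus 62% of subjects reaching 5 µg/mL.

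Section 9.4.3 assigns the non-inferiority tests to the per-protocol set, "while the confirmatory analyses of superiority will be based on the ES".

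**The concern.** Bullet 3 is fully specified: test, sidedness, alpha, sample size, effect and dispersion. A reader should be able to reproduce its power, and cannot do so from the inputs as written. Either the dispersion is mislabelled or the power is wrong.

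The two possibilities differ in consequence. GMC superiority is confirmatory and gates objective 4. If 0.63 is truly a variance, the chance of missing objective 3 under the planning alternative is about 14% rather than 3%, and the overall power claim loses most or all of its margin. If 0.63 is an SD, the trial's planning is sound, but the published dispersion is wrong for anyone who reuses it to plan a later anti-PRP study.

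**Working it through.** **Inputs, all from Section 9.2.** n = 200 per group; one-sided α = 0.025; δ = log10(1.75) = 0.2430; dispersion 0.63; non-inferiority margin −0.301; proportions 46% and 62%.

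**Formula.** Two-sample t-test: SE = SD × √(2/n), non-centrality λ = δ/SE, df = 2n − 2 = 398, critical value 1.966. Power is the probability that a non-central t with parameter λ exceeds 1.966.

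**Objective 3 (GMC superiority), stated power about 97%**

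| Reading of 0.63 | SD | SE | λ | Power |
|---|---|---|---|---|
| Standard deviation | 0.630 | 0.0630 | 3.857 | 97.05% |
| Variance, as written | √0.63 = 0.794 | 0.0794 | 3.062 | 86.3% |

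The SD reading reproduces the protocol's figure. Solving backwards, exactly 97% needs an SD of 0.631 (variance 0.398). Any power that rounds to 97% needs an SD of about 0.62 to 0.64, that is a variance of about 0.38 to 0.41. A variance of 0.63 is well outside that range. By the normal approximation, 97% power with variance 0.63 would need about 315 per group, against 199 with SD 0.63.

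**Could another input explain 97% with variance 0.63?**

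- Exposed Set instead of evaluable subjects: 250 per group, assuming every enrolled child has a result, gives 92.7%.
- One-sided α of 0.05: 92.1%, and it contradicts the stated 2.5%.
- Both together: 96.2%, still short and against two stated inputs.
- Allowing for objective 1: its power is above 99.99% on either reading, so it changes nothing. Requiring an earlier success cannot in any case raise the joint power.

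**Objective 1 (GMC non-inferiority).** δ + 0.301 = 0.544, so λ = 8.63 (SD 0.63) or 6.85 (variance 0.63). Power exceeds 99.99% both ways, so this bullet cannot tell the readings apart.

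**Objective 4 alone (superiority of proportions).** Pooled Z: null SE = √(2 × 0.54 × 0.46/200) = 0.0498; alternative SE = √(0.46 × 0.54/200 + 0.62 × 0.38/200) = 0.0492. Power = Φ((0.16 − 1.96 × 0.0498)/0.0492) = 89.7%. This does not involve 0.63.

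**All four objectives.** Objective 2 is about 99.96% by normal approximation.

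| Combination | SD 0.63 | Variance 0.63 |
|---|---|---|
| Lower bound (1 minus the sum of the four type II errors) | 86.7% | 76.0% |
| Product (independence) | 87.1% | 77.4% |
| Objectives 3 and 4 simulated on the same subjects | 89.2% | 82.9% |

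The simulation draws normal log10 values with cut-points set in each group to keep 46% and 62%. Objectives 1 and 2 are close to certain and barely affect that row.

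**Cross-check on the label.** If concentrations are log-normal with a common SD, then 46%, 62% and a ratio of 1.75 together imply SD = 0.2430/(z(0.62) − z(0.46)) = 0.2430/(0.3055 + 0.1004) = 0.599. That is close to 0.63 and far from 0.794. It is only suggestive, because log-normality is my assumption.

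**The case against.** The strongest reply is that this is a slip of terminology with no consequence. Read as an SD, 0.63 returns the stated 97%, the other powers hold, and nothing in the analysis depends on the planning value, because the ANOVA uses the observed residual variance. This is probably right, and it limits the weight of the point. It does not dispose of it: the documents give no other dispersion figure, the word appears in two bullets, and the alternative, a wrong power, cannot be excluded from the text.

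A second reply is that Section 9.2 does say how the powers combine, since each later bullet states that it allows for earlier objectives. That is fair as far as it goes. The wording describes a sequential calculation, but gives no formula and no assumption about the correlation between the two superiority tests. Under the variance reading, that assumption decides which side of 80% the answer falls on.

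Third, independence is implausible, because objectives 3 and 4 use the same measurement in the same children. This stands. The simulated 82.9% is the more realistic figure, so the 76% to 77% values do not show that the overall claim fails.

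**Conclusion.** The point holds. With the inputs Section 9.2 states, a variance of 0.63 gives 86.3% power for GMC superiority, about 11 points below the reported figure; an SD of 0.63 gives 97.05%. The label and the power cannot both be right. This part rests on no assumption beyond the protocol's own inputs.

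A mislabelled SD is the more likely explanation, and then no stated power changes. If the figure is truly a variance, objective 3 power is overstated, while at least 80% for all objectives is neither guaranteed nor shown to be wrong. Those overall figures depend on the combination rule and, for the simulation, on log10-normal data. Nothing here shows that the trial is too small.

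**What to change.** Check the input in the sponsor's sample-size planning file, then make one of two corrections in Section 9.2:

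- **If 0.63 is the SD:** in bullets 1 and 3, replace the variance wording with a common standard deviation of 0.63 (variance 0.397). All stated powers remain.
- **If 0.63 is the variance:** restate objective 3 power as about 86%, and recompute the power for all objectives with the combination rule given (76.0% lower bound, 77.4% under independence, about 83% when the correlation between the superiority tests is counted).

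The cost is wording in two bullets, or one restated power plus a sentence on how the powers are combined. Enrolment, conduct and the planned analyses are unaffected.

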## 9.3 Analysis Sets

For purposes of analysis, the analysis sets are defined in [Table 7](#).

**Table 7 Analysis Sets**

Analysis Set	Description
Enrolled set	All subjects with a study intervention (either randomised or vaccinated or with a blood draw).
Exposed set (ES)	All vaccinated subjects. Subjects will be analysed according to the intervention they received at Dose 1.
Per protocol set (PPS)	All eligible subjects who received all DTPa-combination study vaccines as per protocol, who had anti-PRP results post-vaccination, who complied with vaccination/blood draw intervals ( Table 8 ), without intercurrent conditions that may interfere with immunogenicity and without prohibited concomitant medication/vaccination. Subjects will be analysed according to the intervention they received at Dose 1.

**Table 8** Intervals Between Study Visits

Interval	Length of interval	Allowed interval
Birth (age is 0 day on birth date) → Visit 1	6 to 12 weeks	42 to 84 days
Visit 1 → Visit 2	60 days	52, 78 days
Visit 2 → Visit 3	30 days	21, 48 days
Birth → Visit 4	365 days	335, 395 days
Visit 4 → Visit 5	30 days	21, 48 days

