### **6.4.5 Blinding and Unblinding**

The laboratory in charge of sample testing will be blinded to the intervention assignment. Codes will be used to link the subject and study (without any link to the intervention attributed to the subject) to each sample.

In case of an emergency, the investigator has the sole responsibility for determining if unblinding of a subject's treatment is warranted. Subject safety must always be the first consideration in making such a determination. If the investigator decides that unblinding is warranted and subject treatment is unblinded, GSK must be notified within 24 hours after breaking the blind. The date and reason that the blind was broken must be recorded in the source documentation and eCRF, as applicable. A subject may continue in the study if that subject's intervention assignment is unblinded.

Unblinded monitors and, in the event of a Quality Assurance audit, the auditor(s), will be allowed access to unblinded study treatment information records at the site(s) to verify that randomisation/dispensing has been done accurately.

Despite the fact that this is a single-blind study, the data management and biostatistics teams will remain blinded to the study treatment until after the final database lock. No unblinded data summaries (presented by treatment) will be available prior to the final database lock. An independent unblinded Biostatistician will be identified to review potentially unblinding information ahead of the final database lock, e.g., randomisation specifications and schedule.

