5. ANALYSIS SETS

Agreement and authorization of subjects included/excluded from each analysis set will be conducted prior to the unblinding of the study.

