5.1. PROCESS FOR ANALYSIS SET ASSIGNMENT

- Definitions for analysis sets are provided below.
- Prior to database lock, a transfer of raw data from the eCRF will occur, and subjects will be assigned to analysis sets in accordance with the definitions in this SAP and the available data at that time. However, the protocol deviations will be monitored continuously throughout the study.
- Listings presenting subjects excluded from each preliminary analysis set and reasons for exclusion will be prepared for sponsor review ahead of database lock in order to allow appropriate related data

Document : \\quintiles.net\enterprise\Apps\sasdata\SASb\SAS\GSK\Infanrix\PPD\Biostatistics\Documentation\NSAP

Author: PPD Version Number: 1.0

Version Date: [07JAN2021]

Template No.: CS_TP_BS016 Revision 6

Reference: CS_WI_BS005

Effective Date: 02Dec2019

queries to be issued.

- Listings presenting subjects excluded from each final analysis set and reasons for exclusion will be prepared for sponsor review ahead of unblinding for a final review and approval. However, for deviations that can only be assessed after unblinding (such as vaccination errors or pre and post booster samples), these will be reviewed after unblinding.
- A Data Review meeting will be held to confirm analysis set assignment for each subject and any changes will be recorded. Changes will be implemented, and an updated analysis set assignment will be approved by the sponsor.
- Sponsor authorization of the analysis sets will be necessary to unblind the data after database lock. Once approved, analysis sets will be finalized, and the database will be locked.
- After database lock, the final analysis sets will be derived using the final study data, i.e., clinical database (CRF), external vendor data (immunogenicity results) and protocol deviations log.

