5.3. EXPOSED SET [ES]

The exposed set (ES) will include all vaccinated subjects with ICF and exclude any fraudulent data. Subjects will be analysed according to the intervention they received at Dose 1.

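### Superiority is tested on the Exposed Set grouped by the vaccine received at Dose 1, and no analysis by randomised group is planned (minor)

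*Protocol*

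**What the plan says.** Protocol 9.4.3 puts non-inferiority on the Per Protocol Set (PPS) and states that "the confirmatory analyses of superiority will be based on the ES". SAP Table A and SAP 16.1.1 agree.

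Protocol Table 7 defines the Exposed Set (ES) as every vaccinated subject and adds: "Subjects will be analysed according to the intervention they received at Dose 1". SAP 5.3 narrows membership slightly ("The exposed set (ES) will include all vaccinated subjects with ICF and exclude any fraudulent data") and keeps the same Dose 1 grouping rule. Neither document plans a superiority analysis by randomised group.

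On timing, SAP 5 says: "Agreement and authorization of subjects included/excluded from each analysis set will be conducted prior to the unblinding of the study". SAP 5.1 makes an exception in its bullet on listings of subjects excluded from the final sets: "for deviations that can only be assessed after unblinding (such as vaccination errors or pre and post booster samples), these will be reviewed after unblinding".

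On blinding, Protocol 6.4.5 says that "the data management and biostatistics teams will remain blinded to the study treatment until after the final database lock". It also provides for an independent unblinded biostatistician and a laboratory that does not know the assignment. The treatment number given is recorded in the eCRF at each vaccination (Protocol Table 3).

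**The concern.** A superiority claim draws its protection against bias from comparing the groups that randomisation formed. Here allocation is by minimisation on country and maternal immunisation, and the GMC model adjusts for both factors. The groups compared, however, are defined by something that happens after randomisation: which hexavalent vaccine was injected at Dose 1.

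Two features make the rule a poor fit for these two objectives.

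- **It acts mainly on superiority.** The PPS requires the study vaccines to be given as per protocol, and SAP 9.2.2 allows exclusion for inaccurate dosing. A subject with a Dose 1 error would normally leave the non-inferiority analysis but stay in the ES, in the other arm.
- **It is not a full as-treated rule either.** The endpoint follows three doses, and each later dose has its own treatment number (Protocol 6.4.4). A subject with an error at Dose 1 who then receives the assigned vaccine twice is still analysed under the Dose 1 vaccine.

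The SAP is also not uniform. Its listing conventions (Appendix 1) sort by vaccine group and use the intervention received only for safety outputs.

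**Working it through.** **Inputs.** From Protocol 9.2: 200 evaluable subjects per group; one-sided 2.5% level; GMC ratio 1.75, i.e. 0.2430 in log10; spread 0.63 in log10; 62% (Infanrix hexa) and 46% (Vaxelis) at or above 5 µg/mL. From Protocol 9.4.3: Miettinen-Nurminen interval for the percentage difference. Assumed, because the documents are silent: 0 to 5 Dose 1 errors in step 2, and 0 to 5% per arm in step 3.

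**1. The plan's own power.** For GMC superiority, the standard error is 0.63 × √(2/200) = 0.063 and the noncentrality is 0.2430/0.063 = 3.86. The noncentral t with 398 degrees of freedom gives 97.0%, matching the stated figure of about 97%. This treats 0.63 as a standard deviation. The protocol calls it a variance, and that reading gives 86.3%. This is a separate point, but it decides which figure is used below. For percentage superiority, the pooled Z test with 200 per group gives 89.7%.

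**2. Effect of reassigning subjects on the percentage objective.** Superiority requires the Miettinen-Nurminen 95% lower limit to exceed 0.

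| Inv_group | Com_group | Difference | Lower limit |
|---|---|---|---|
| 112/200 | 92/200 | 10.0 | +0.19 |
| 111/199 (one responder moved out) | 93/201 | 9.5 | −0.30 |
| 112/199 (one non-responder moved out) | 92/201 | 10.5 | +0.70 |
| 124/200 (planned rates) | 92/200 | 16.0 | +6.24 |
| 119/195 (five responders moved out) | 97/205 | 13.7 | +3.9 |

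Differences and limits are in percentage points. One subject shifts the limit by about 0.5 points: 0.19 − (−0.30) = 0.49 and 0.70 − 0.19 = 0.51. The first row was chosen to lie at the boundary. The last row takes the planned rates and moves five subjects in the least favourable direction for Infanrix hexa; superiority still holds.

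**3. Cost of analysing as randomised.** Suppose a share e of each arm received the other vaccine throughout and is kept in its randomised group. The log10 difference becomes 0.2430 × (1 − 2e). The variance becomes 0.63² + e(1 − e) × 0.2430². The percentages become 62(1 − e) + 46e and 46(1 − e) + 62e.

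| e | Errors per arm | GMC power | Percentage power |
|---|---|---|---|
| 0 | 0 | 97.05% | 89.7% |
| 0.5% | 1 | 96.8% | 89.1% |
| 1% | 2 | 96.47% | 88.5% |
| 2% | 4 | 95.8% | 87.2% |
| 5% | 10 | 93.2% | 82.6% |

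At 1% the loss is 97.05 − 96.47 = about 0.6 points for GMC and 89.7 − 88.5 = 1.2 points for the percentage. If 0.63 is a variance, GMC power runs from 86.3% (e = 0) to 84.9% (1%) and 78.3% (5%).

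**The case against.** The case for leaving the rule alone has four parts.

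- **The two groupings may coincide.** They differ only for subjects given the other hexavalent vaccine at Dose 1. Allocation is central, no error rate is given, and with no errors the results are identical. This stands, and it limits the size of the point.
- **The boundary example proves little.** At 112/200 versus 92/200, one changed result with no reassignment (111/200 versus 92/200) gives −0.31. The example shows closeness to the boundary, not a particular weakness of as-received grouping. This also stands.
- **Regrouping does not give a full intention-to-treat analysis.** The ES omits randomised but unvaccinated subjects, and missing post-booster results are not imputed. With 20% assumed non-evaluable, missing results could far outnumber allocation errors. This is true. It is a reason not to oversell the change, not a reason against it.
- **Bias through knowledge of treatment is remote.** The investigator knows the assignment, but the endpoint is a concentration measured by a blinded laboratory. Nothing shows how a Dose 1 error would come to depend on a response measured about 11 months later. This stands.

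A reader might also infer from SAP 5.1 that a subject's group can be settled after treatment codes are known. The documents do not support that. The grouping rule is fixed in advance and leaves no discretion, and the treatment number given is a recorded fact. The exception for vaccination errors sits in a bullet about exclusions from sets and does not mention moving subjects between arms. At most, a Dose 1 error could first be recognised in that later review.

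**Conclusion.** The point holds in principle and is minor in size. As written, both superiority tests compare groups defined by the vaccine received at Dose 1, and nothing in the plan shows the result by randomised group.

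The consequence is nil without Dose 1 errors. It could change the percentage conclusion only if the lower limit lies within about half a point of zero per misallocated subject. At the planned rates, five errors would not change it. For the GMC objective, only the power cost of regrouping was calculated, not the effect of individual reassignments.

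These sizes rest on 200 subjects per group, 0.63 as a standard deviation, and assumed error counts and rates that the documents do not supply. The conclusion does not depend on any claim that group membership is decided after unblinding.

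**What to change.** In Protocol Table 7 and 9.4.3, and in SAP 5.3 and 16.1.1, state that superiority (objectives 3 and 4) is analysed on the Exposed Set by randomised group. Apply the same grouping to the ES immunogenicity summaries in SAP 16.2, so that two differently grouped post-booster ES results do not appear side by side. Keep grouping by intervention received at Dose 1 for safety outputs, and show the as-received superiority result as a sensitivity analysis.

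The cost is a short text change in both documents and one extra table. The randomised group is already held in the IVRS, and at an error rate up to about 1% the sample size need not change. The downside is the slight dilution shown above if errors occur. For superiority, the change also removes any question about reviewing vaccination errors after unblinding, because the randomised group is fixed before an error can happen.
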